4.5.5 Dose Escalation and Cohort Progression

For Cohorts 1 to 3, decisions relating to dose escalation will be made by the sponsor (including the medical monitor, the safety physician, the project medical director and additionally final approval by the MedImmune SMC which includes internal and external experts). These reviews based on a review of all cumulative safety data, will occur after at least 18 subjects have completed dosing on Day 29. Once recruitment to Cohort 4 is initiated, an initial 18 of the planned total of 54 subjects for this cohort, will be recruited (12 CAM-3001 and 6 placebo); once at least 6 of these subjects have been exposed to study treatment for the entire treatment period (Day 85) and no safety concerns have been detected, recruitment will resume to enrol the remaining number of subjects planned for this cohort.

Note that where data is available from subjects in Japan, these data will be included in the safety reviews.

The safety evaluations for dose escalation (Cohorts 1 to 3) and completion of recruitment (Cohort 4) will include cumulative, blinded safety information; including AEs, SAEs, events of special interest (ESIs) including pulmonary function testing and DLCO, laboratory data and any associated information.

Events of special interest are events that might be anticipated considering the mechanism of action of CAM-3001, or might be associated with monoclonal antibodies in general. For this protocol the ESIs are defined as: reproductive toxicity, haematopoietic effects, susceptibility to infection, pulmonary alveolar proteinosis (PAP), anaphylactoid-like and anaphylactic

Protocol MI-CP219: Amendment 3 Final

CAM-3001 reactions (see Investigator's Brochure for detailed information). Specifically, the following ESIs are defined below and will be closely monitored by the investigator/designee and will be reviewed by the medical monitor throughout the study:

- Neutropenia; neutrophils $< 1.0 \times 10^9$ /L unless the cause for neutropenia can be clearly attributed to causes other than investigational product.
- Serious or life threatening infections, or opportunistic infection requiring hospitalisation, or septic shock unless a relationship to investigational product can be clearly excluded.
- Acute hypersensitivity reaction severe or life-threatening hypersensitivity reaction (as defined in Appendix 1) unless a relationship to investigational product can clearly be excluded.
- Death or life threatening AE, which is considered to be possibly attributable to investigational product.
- Clinically significant respiratory diseases and deterioration of pulmonary function and DLCO, confirmed by the study pulmonologist, considered to be possibly attributable to investigational product.

The sponsor may recommend that dose escalation continues as defined below:

- If none of the events described above occur, and there are no other observations 1) suggesting that there may be a change to the risk/benefit profile of the product; or
- If, one or more ESIs (including laboratory abnormalities) are observed but these do 2) not represent a material change to the risk/benefit profile of the product as described by the Investigator Brochure and as agreed by the sponsor.

Conversely, even if no ESIs are observed but there are any other reasons for the sponsor to believe that there has been a material change to the risk-benefit of the product which requires a change in the conduct of the study, then the study will be stopped immediately until an update can be provided to the IRB/IEC along with a recommendation for further action.

4.5.6 **Treatment Compliance**

MedImmune

Investigational product is administered by study site personnel, who will monitor compliance.

MedImmune CAM-3001 **4.6 Subject Status**

Subject Completion

The primary analysis will be performed when all subjects have completed the treatment period through Day 85. An individual subject will be considered to have completed the safety follow-up of the study if the subject was followed up through Day 169, regardless of the number of doses of investigational product that was received.

It should be specified on the source document whether or not the subject completed the study safety follow-up procedures through Day 169.

Subjects will be considered not to have completed the study if one of the following conditions applies:

- Withdrawal of consent: If consent for follow-up is withdrawn, the subject will not receive any further investigational product or further study observation. Note that the subject may need to undergo additional tests or tapering of treatment to withdraw safely. Subjects who withdraw consent will be asked to give a reason; however the subjects may decline to provide this information.
- Lost to follow-up: Subjects will be considered lost-to-follow-up only if no contact has been established by the time the study is completed such that there is insufficient information to determine the subject's status on Day 169.

Note: Subjects refusing to return to the site or to continue participation in the study should be documented as "withdrawal of consent" rather than "lost to follow-up." Investigators should document attempts to re-establish contact with missing subjects throughout the study period. If contact with a missing subject is re-established, the subject should not be considered lost-to-follow-up and any evaluations should resume according to the protocol.

4.7 Study Completion

Study completion is defined as the date of the last protocol-specified visit/assessment for the last subject in the study. All materials or supplies provided by the sponsor will be returned to the sponsor or designee upon study completion, as directed by the site monitor. The investigator will notify the IRB/IEC when the study has been completed.

5 Assessment of Efficacy and Clinical Pharmacology

5.1 Efficacy and Clinical Pharmacology Parameters

5.1.1 Efficacy Parameters

5.1.1.1 Primary Efficacy Endpoint

The effect of CAM-3001 on the response rate in terms of improvement in DAS28 c-reactive protein (CRP) score on the day of last dose of investigational product (Day 85) will be evaluated. According to the European League Against Rheumatism (EULAR) response criteria an improvement from baseline (Day 1) in DAS28(CRP) of more than 1.2 would be considered a good response in subjects experiencing low disease activity (baseline DAS28 < 3.2) and a moderate response in subjects experiencing medium to high disease activity (baseline DAS28(CRP) \geq 3.2). A responder will be defined as a subject experiencing a decrease of more than 1.2 from their baseline DAS28(CRP) score, on the day of last dose of investigational product (Day 85 per protocol).

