4.2 Subject Selection

The subjects in this study will be male or female adults with RA as defined by the 1987 American College of Rheumatology (ACR) classification criteria, and at least moderately active disease, as defined by Disease Activity Score (DAS) 28 criteria (DAS \geq 3.2), despite treatment with methotrexate for at least 12 weeks prior to Screening, which has been kept at a stable dose for at least 4 weeks (7.5 to 25 mg/week).

The investigator (physician) or qualified designee will discuss the study with a subject who is considered a potential candidate for the study and provide the subject with the study-specific informed consent form approved by the Institutional Review Board (IRB)/ Independent Ethics Committee (IEC). The investigator or designee will address any questions and/or concerns that the subject may have and, if there is continued interest, will secure written informed consent for participation in the study. Written informed consent and any locally required authorisation (eg, Health Insurance Portability and Accountability Act [HIPAA] authorisation in the USA, European Union [EU] Data Privacy Directive authorization in the EU), will be obtained prior to conducting any protocol-related procedures, including screening evaluations. See Section 10.3 for additional details concerning informed consent.

MedImmune CAM-3001 **4.2.1** Inclusion Criteria

Subjects must meet *all* of the following criteria:

- 1) Male or female
- 2) Age 18 through 80 years at the time of Screening
- 3) Signed and dated informed consent, prior to receipt of any study medication or any study related procedures.
- 4) A diagnosis of adult onset RA of at least 3 months duration as defined by the 1987 ACR classification criteria (Arnett et al, 1988).
- 5) Treatment with methotrexate (7.5-25 mg/week) for at least 12 weeks and at stable and tolerated doses for at least 4 weeks prior to Screening.
- 6) Positive anti-cyclic citrullinated peptide (CCP) IgG antibodies (> 5 IU/mL) and/ or rheumatoid factor (> 14 IU/mL) at Screening.
- 7) Subjects must receive \geq 5 mg/week folic acid as a single or divided dose during the study.
- 8) At least moderately active disease as defined by $DAS28 \ge 3.2$ at Screening and Baseline (see Section 5.3.4.1; Smolen et al, 2003).

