5.3.4.1 DAS28

The DAS28(CRP) has been validated against radiographic progression and physical function (HAQ-DI) and the validation profile is similar to the DAS28 Erythrocyte Sedimentation Rate (ESR) (Wells et al, 2009). In this study both CRP and ESR will be collected. Subjects are required to have at least moderately active disease as defined by DAS28 \geq 3.2 at Screening and Day 1 in order to be included in this study. The investigator will calculate DAS28(CRP) for Screening and DAS28(ESR) for Day 1 to assess this criterion.

The DAS28 considers 28 of the 68 tender joint count (TJC) and 28 of the 66 swollen joint count (SJC), general health (GH) using patient assessment of disease activity using the numerical rating scale with 0 = best, 100 = worst, plus levels of CRP (mg/L) or ESR (mm/hour).

DAS28(CRP) values will be calculated as follows (Wells et al, 2009):

DAS28(CRP) = 0.56 * sqrt(TJC28) + 0.28 * sqrt(SJC28) + 0.014*GH + 0.36 ln(CRP+1) + 0.96

DAS28(ESR) values will be calculated as follows:

DAS28(ESR) = 0.56 * sqrt(TJC28) + 0.28 * sqrt(SJC28) + 0.70*ln(ESR) + 0.014*GH

DAS28 will be categorised using the EULAR response criteria:

Protocol MI-CP219; Amendment 3 Final

Baseline DAS Score	Level of Improvement from Baseline (Day 1)									
	> 1.2	\geq 0.6 to \leq 1.2	< 0.6							
< 3.2	Good response	Moderate response	No response							
\geq 3.2 to \leq 5.1	Moderate response	Moderate response	No response							
> 5.1	Moderate response	No response	No response							

Table 5.3.4.1-1DAS28 Improvement

DAS = Disease Activity Score

DAS28 defined remission is DAS28 of < 2.6. Low disease activity is < 3.2 and high disease activity is > 5.1.

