7.3.1 Primary Endpoint

7.3.1.1 Efficacy

The primary efficacy objective will assess DAS28 response rates of CAM-3001 treated subjects compared with subjects who received placebo on the day of last dose of investigational product (Day 85). According to the EULAR response criteria an improvement from baseline in DAS28 of more than 1.2 would be considered a good response in subjects experiencing low disease activity (baseline DAS28 < 3.2) and a moderate response in subjects experiencing medium-to-high disease activity (baseline DAS28 \geq 3.2). A responder will be defined as a subject experiencing a decrease of more than 1.2 from their baseline DAS28 score, on the day of last dose of investigational product (Day 85).

Evaluable subjects will be cross-classified in a two-by-two contingency table according to their combined treatment group (CAM-3001 or Placebo) and by their responder status (Yes or No). The DAS28 response rate at Day 85 between combined CAM-3001 and combined placebo treatment groups will be compared using a two-sided Fisher's exact test.

Following the above comparison between the combined CAM-3001 and combined placebo treatment groups, each applicable dose cohort and the combined placebo group will be compared. These comparisons at the dose cohort level are not powered and as such their results will be considered in an exploratory setting. There will also be no adjustment for multiplicity. A 95% confidence interval of difference in DAS28 response rate between CAM-3001 and placebo treatment groups will be computed for each dose cohort to estimate the effect size of each CAM-3001 dose level.

The DAS28 response rate at Day 29 between CAM-3001 and placebo will also be compared using a Fisher's exact test.

To check the sensitivity of the comparisons, all the above analyses will be repeated over the respective cohort groupings but in the more restrictive ATP population. Due to the definition of the ATP population no imputation of the DAS28 score is needed for these analyses.

MedImmune CAM-3001 **7.3.1.2 Safety**

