7.3.2.1 Disease Activity

The major clinical measures of RA disease activity will be summarised descriptively by treatment group and time and include ACR20, ACR50, and ACR70 responses and DAS28 responses, including moderate and good responses, and complete clinical responses.

The ACR20, ACR50, and ACR70 binary responses will be compared between the CAM-3001 and placebo treatment groups using the Fisher's exact test at each study time point.

Protocol MI-CP219; Amendment 3 Final

The ACR response at Days 29, 43, 57, 71, 85, 99, 113, and 169 will also be analysed as a continuous variable. An appropriate continuity correction maybe applied if the data are interval bound or discrete. The ACR response will be compared between the CAM-3001 and placebo treatment groups using a repeated measures model.

The DAS28 responses at various study time points other than Day 29 and Day 85 will also be compared between the CAM-3001 and placebo treatment groups using the methodology described in the secondary endpoint analysis section, although no imputation will be used in these analyses.

The DAS28 responses will be compared between the CAM-3001 and placebo treatment groups according to the EULAR response criteria at certain study time points using a Cochran-Mantel-Haenszel test.

All the modelling and other comparative analysis described above will be conducted over the appropriate dose cohort groupings and time points as noted above. Each analysis will first compare between the combined CAM-3001 and combined placebo treatment groups. The analysis will then be conducted separately comparing combined placebo group and each of the applicable dose cohorts. Most of the above analysis will be conducted over both the evaluable and ATP populations. Details of all these analyses will be described in the SAP.

The predicted DAS28 and ACR values from the models above will be compared to the actual values observed at Day 85, and Day 169 for subjects in Cohort 3 as they become available. This will test the predictive capability of such models and will also help calibrate them as necessary.

Core components of the ACR and DAS28 responses will be summarised descriptively by treatment group and time and change from baseline. Levels of rheumatoid factor, anti-CCP antibodies, ESR, and subject's need for rescue corticosteroid therapy will be summarised descriptively by treatment group and time point and change from baseline.

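### The EULAR good-response category is empty or nearly empty, because it requires a baseline DAS28 below 3.2 and the entry criteria require 3.2 or more

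*Protocol*

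**What the plan says.** **The response rule.** Section 5.3.4.1 states that "DAS28 will be categorised using the EULAR response criteria" and gives Table 5.3.4.1-1. Its columns are the improvement from Day 1 (more than 1.2; 0.6 to 1.2; less than 0.6). Its rows are headed by the baseline score (below 3.2; 3.2 to 5.1; above 5.1). A good response appears in one cell only: baseline below 3.2 with improvement above 1.2. Section 5.1.1.1 puts this in words: such an improvement is "considered a good response in subjects experiencing low disease activity (baseline DAS28 < 3.2) and a moderate response" at higher baselines. Section 7.3.1.1 repeats it: the change "would be considered a good response in subjects experiencing low disease activity (baseline DAS28 < 3.2").

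**The entry rule.** Inclusion criterion 8 in 4.2.1 reads "At least moderately active disease as defined by $DAS28 \ge 3.2$ at Screening and Baseline". Section 5.3.4.1 adds how this is checked: "The investigator will calculate DAS28(CRP) for Screening and DAS28(ESR) for Day 1 to assess this criterion".

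**The use.** Section 7.3.2.1 plans to summarise "DAS28 responses, including moderate and good responses, and complete clinical responses", and to compare CAM-3001 with placebo on the EULAR categories by a Cochran-Mantel-Haenszel test. Section 5.3.4.1 separately states that "DAS28 defined remission is DAS28 of < 2.6".

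**The concern.** The only row of the table that can produce a good response describes subjects whom criterion 8 keeps out. The plan thus names a three-level outcome, and a summary of good responses, whose top level is unreachable or nearly so. The grading also runs against the protocol's own definitions: a subject who reaches remission from a high baseline gets the same grade as one who improves by just over 1.2 and still has active disease.

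The analysis at stake is the secondary EULAR comparison, overall and by dose cohort. A good-response rate of about 0% in every arm would say nothing about the drug, yet it could be read as a lack of strong responders.

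**Working it through.** **1. The plan's own figure.** Section 7.4 states 86% power for 10% against 30% with 60 placebo and 120 active subjects (two-sided Fisher's exact test, alpha 0.05), and 92% for 72 and 144. Exact enumeration gives 87.8% and 93.6%, within 2 points of the stated values. This endpoint uses only a decrease of more than 1.2, with no good/moderate split, so nothing below changes it.

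**2. The table applied to eligible baselines.** The table was coded and run over baselines from 3.2 to 9.4 in steps of 0.1, with improvements from -2.0 up to the largest the DAS28(CRP) floor of 0.96 allows. Result: 0 good, 2,723 moderate, 1,939 none. These are grid points, not expected subjects.

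**3. Single cases.**

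| Baseline to visit | Improvement | Under the table | Same cut-offs on attained score |
|---|---|---|---|
| 6.0 to 2.4 | 3.6 | moderate | good |
| 4.5 to 2.5 | 2.0 | moderate | good |
| 5.5 to 4.7 | 0.8 | none | moderate |

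The first two end below 2.6, which is remission under 5.3.4.1.

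**4. The exception.** Day 1 entry is checked with DAS28(ESR), while 5.1.1.1 sets the response baseline on DAS28(CRP). Take TJC28 = 2, SJC28 = 2, GH = 30, CRP = 3 mg/L, ESR = 30 mm/hour:

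- shared terms: 0.56 × √2 + 0.28 × √2 + 0.014 × 30 = 0.792 + 0.396 + 0.420 = 1.608
- DAS28(ESR) = 1.608 + 0.70 × ln 30 = 1.608 + 2.381 = 3.99, which passes Day 1
- DAS28(CRP) = 1.608 + 0.36 × ln 4 + 0.96 = 1.608 + 0.499 + 0.96 = 3.07, which is below 3.2

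Such a subject must also have had a DAS28(CRP) of at least 3.2 at Screening. The documents give no distribution, so a range was assumed: mean DAS28 4.0 to 5.5, between-subject SD 1.0, visit-to-visit SD 0.5, ESR minus CRP offset 0.2 to 0.7 with SD 0.4 or 0.7. About 0.5% to 8% of eligible subjects then have a Day 1 DAS28(CRP) below 3.2. To be graded good they must still improve by more than 1.2, that is, end below 3.2 - 1.2 = 2.0.

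**5. Size of the misgrading.** Assumed: baseline mean 5.0 or 5.8, SD 1.0, at least 3.2 at entry; SD of change 1.1. The mean improvement m is set so that the share improving by more than 1.2 equals the protocol's rate p: m = 1.2 - z(1-p) × 1.1.

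- placebo, p = 10%: m = 1.2 - 1.282 × 1.1 = -0.21
- active, p = 30%: m = 1.2 - 0.524 × 1.1 = 0.62

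| Baseline mean | Good under table | Good on attained score, placebo / active | Subjects changing category, placebo / active | Test power, table / attained |
|---|---|---|---|---|
| 5.8 | 0% | about 2% / 8% | about 6% / 15% | 91% / 93% |
| 5.0 | 0% | about 4.5% / 15% | about 8% / 22% | 93% / 95% |

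Power is for a row-mean-score Cochran-Mantel-Haenszel test with 120:60 at alpha 0.05. The 0% holds in this model because entry and grading use one score.

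**The case against.** The strongest reply is that little depends on this table. The primary responder rule does not use it. Section 7.3.2.1 leaves details to the SAP, and the dose-cohort comparisons of the primary endpoint are declared unpowered and exploratory. Strong responders remain visible elsewhere: remission and low disease activity are defined in 5.3.4.1, and 7.3.2.1 also plans complete clinical responses, ACR20, ACR50 and ACR70, a continuous ACR analysis and change in the core components. All of that stands and limits the severity. It does not remove the defect, because the protocol does not leave the classification open: it fixes it in three places. A SAP that follows the protocol inherits the empty category, and one that departs from it contradicts the protocol.

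Four stronger readings are tempting and not supported:

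- **That a good response is strictly impossible.** This is true only if one DAS28 version serves both Day 1 entry and grading. With ESR for entry and CRP for the response baseline, a few subjects could qualify.
- **That the primary endpoint or its power is compromised.** The sentence sits in the primary-endpoint sections, but the rule there is a decrease of more than 1.2.
- **That dose selection loses its main discriminator.** The other measures listed above remain.
- **That a quarter or more of subjects are misgraded.** Assuming mean improvements of 1.0 and 1.5 with baseline mean 5.0 gives 23% and 37% good responders on the attained score. Those means imply about 43% and 61% improving by more than 1.2, against the 10% and 30% the protocol assumes.

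A last objection is that the documents show an unreachable category, not which row variable was intended, and that grading 5.5 to 4.7 as no response is simply what the table says. That is fair. The case for the attained score rests here on the protocol's own definitions of low disease activity and remission. Dropping the good category would also remove the contradiction, but would give up an outcome that 7.3.2.1 plans to report.

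**Conclusion.** The point holds as a definition error in a secondary endpoint. Table 5.3.4.1-1 and the sentences in 5.1.1.1 and 7.3.1.1 cannot be squared with criterion 8: the good category is empty or nearly empty, and the EULAR test in 7.3.2.1 is in effect two-level. That conclusion needs no assumption beyond the documents.

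The sizes do rest on assumptions, since the protocol gives no DAS28 mean or SD. Within the ranges shown, about 2-5% of placebo and 8-15% of active subjects would be good responders on the attained score, and about 6-8% and 15-22% would change category. The loss of power is small, about 2 points. The main harm is to what the results would mean, with remission graded as moderate and good responses reported at about zero by construction. Primary responder rule, sample size and power are unaffected.

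**What to change.** - In Table 5.3.4.1-1, replace the baseline row heading by the DAS28 attained at the assessed visit, keeping the cut-offs and the improvement columns.
- Change the EULAR sentences in 5.1.1.1 and 7.3.1.1 to match, so that low or medium-to-high activity refers to the attained score.
- State which DAS28 version, CRP or ESR, sets the category.
- Leave the primary responder rule as it is.

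Re-heading the rows also moves some subjects from none to moderate (5.5 to 4.7, for example), so the amendment should say that the whole classification changes, not only the good cell.

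The cost is one table heading, two sentences and a line on the version, with no new data, visits or subjects. It should be done before the sponsor is unblinded to the non-Japanese data at the Day 85 analysis; a redefinition after that would look driven by the results.
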